8.2. Secondary Efficacy Endpoints and Analyses

8.2.1. Change in FIX activity levels from pre-dose

Actual and change from baseline (including maximum absolute change from baseline) values for FIX activity level will be summarized by time point for the PK and the Safety Population. Different PK parameters will be summarized as well as described in [Section 9](#).

8.2.2. Occurrence of clinically significant levels of thrombogenicity markers resulting from SC administration of CB2679d

The following thrombogenicity markers during the treatment period will be assessed for the PD and the Safety Population:

- Fibrinogen,
- D-dimer,
- F1+2,
- TAT

Detailed PD analysis is described in [Section 10](#).

8.3. Additional Analyses

In addition to the primary endpoint analysis, the number and percentage of subjects with a FIX activity level >30% and >50% will be summarized during treatment period for the PK and the safety population.

This document is confidential.

Statistical Analysis Plan for Interventional Studies
Sponsor: Catalyst Biosciences, Inc.; Protocol No.: DLZ-201

9. Analysis of Pharmacokinetics

PK analysis will be performed by Catalyst Biosciences, Inc. using compartmental and non-compartmental analysis in Demitasse 2000 (M.Lee, UCLA). The PK Tables, Listings, and Figures (TLFs) will be produced using SAS statistical package version 9.4 or higher. PK analysis will be performed for the PK and the Safety Population.

9.1. PK Sampling Schedule

PK sampling schedule will be specific to each dose administration. The PK data will be measured as FIX activity levels.

During treatment period: On Day 1, PK assessments will be done at pre-IV dose and repeated 35 (\pm 5) minutes later prior to the SC dose. Subsequent PK assessments will be performed pre-dose on days 2, 3, 7, 14, 21 and 28.

Washout Period: PK assessments will be done on Days 29, 30, 31, 32 and 33. Daily FIX activity levels will be measured, unless FIX activity level is known to be < 5% as measured by local laboratory.

9.2. Plasma PK Endpoints

Various pharmacokinetic parameters will be calculated as listed below, including:

- clearance (CL) (from Day 28 and subsequent samples during washout)
- volume of distribution at steady state (Vz) (from Day 28 and subsequent samples during washout),
- Highest recorded clotting activity level after nadir value from the IV infusion
- and terminal (beta phase) half-life $t_{1/2}$, will be calculated from Day 28 and subsequent samples during washout

A semiparametric model described by Lee et al. (Lee et al, 1990) will be used to calculate the terminal $t_{1/2}$. This analysis will be performed using the program Demitasse 2000 (Lee et al, 1997). Other parameters will be calculated using a standard non-compartmental approach.

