Interim results showed PK and activity of CB2679d as 22-fold greater potency over BeneFIX® and longer mean residence time. Single-dose bioavailability was 18.2-23.6%, SC beta $t_{1/2}$ was 66-103 hours and time that CB2679d is present at the maximum concentration in serum (T_{max}) was 6-24 hours. One subject reported transient fever and a mild SC injection site reaction. Cohort 4 was omitted as sufficient data had been gained from single dosing SC in Cohorts 2 and 3. The SC dose in Cohort 5 was reduced from 300 IU/kg to 150 IU/kg daily. PK and activity

Dalcinonacog alfa_DLZ-201 VERSION 2.0, Amendment 1

levels after 6 daily doses in 5 subjects reached a median of 15.7% [interquartile range 14.9% to 16.6%] Four of 5 subjects had levels above 12%. Half-life was 63.2 hours [interquartile range 60.2 to 64.0 hours]. The interim study results support the aim of achieving normal or high mild hemophilia FIX levels in individuals with hemophilia B with repeated SC dosing. Mild pain, erythema and redness was reported at the injection site in initial injections and not a later injection. One subject reported these adverse events to be moderate for the first 2 injections and mild thereafter. An IV loading dose has been added to cohort 6 in this study to see if it eliminates injection site adverse events as they are believed to be due to low FIX levels because of washout of prior treatment ([Figure 2](#)).

The nadir activity after IV plus SC dosing was 20% in both subjects in cohort 6 and thereafter levels increased to >30%. It is clear that the IV loading dose increased the bioavailability of SC CB2679d by increasing the saturation of the extravascular compartment and resulted in greater activity levels than simple addition of SC to IV activity. Neutralizing antibodies developed in both subjects (transiently in one subject). A root cause analysis determined that the most likely cause was a 3-month gap between dosing in cohort 5 and cohort 6 in these 2 participants ([Figure 3](#)).

FIGURE 2. CB2679D PHASE 1/2 OPEN LABEL STUDY DESIGN

[figure not shown]

IV, intravenous; SC, subcutaneous.

^aFirst SC dose 30 minutes post-IV.

Dalcinonacog alfa_DLZ-201 VERSION 2.0, Amendment 1

FIGURE 3. CB2679D PHASE 1/2 STUDY: COHORT 5 & 6 FIX ACTIVITY RESULTS

Dalcinonacog alfa_DLZ-201 VERSION 2.0, Amendment 1

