11.12. Follow-up difficulties – Diary Data

Difficulties due to hemophilia after last dose of study drug will be listed.

This document is confidential.

Statistical Analysis Plan for Interventional Studies
Sponsor: Catalyst Biosciences, Inc.; Protocol No.: DLZ-201

12. Interim Analyses

No interim analysis is conducted during the study.

This document is confidential.

SAP Version: V1.0, 24-May-2019
Controlled Document ID: **3903A.01**, Effective Date 29-Oct-2018
Filing requirements: TMF

Page 31 of 44

Statistical Analysis Plan for Interventional Studies
Sponsor: Catalyst Biosciences, Inc.; Protocol No.: DLZ-201

13. Changes from Analysis Planned in Protocol

According to the protocol, "Occurrence of antibody formation resulting in a endogeneous decreased level of FIX" and "Occurrence of a clinical thrombotic event not attributable to another cause" are listed below efficacy assessment. For the statistical analysis they will be considered as safety endpoints.

The definition of the PK and PD populations in [Sections 5.3 and 5.4](#) used for the efficacy endpoint analysis is different from the population description in the protocol.

There have been some changes in the PK section of this SAP as compared to what is presented in the protocol. The protocol requires derivation of area under the curve, concentration maximum, time that studied drug is present at the maximum concentration (Tmax) and T_{max} for the FIX activity levels which is not possible due to limited sampling and nature of the study. Instead, highest recorded activity level after nadir value from the IV infusion will be reported. Furthermore, CL and Vd will only be possible to derive for Day 28 and subsequent samples during the washout period. The detail of these changes is described into [Section 9.2](#) of this SAP.

This document is confidential.

Statistical Analysis Plan for Interventional Studies
Sponsor: Catalyst Biosciences, Inc.; Protocol No.: DLZ-201

14. Reference List

Sean Wallis. Binomial Confidence Intervals and Contingency Tests:Mathematical Fundamentals and the Evaluation of Alternative Methods, Journal of Quantitative Linguistics. 2013; 20:3, 178-208.

Lee ML, Poon Wai-Yin, Kingdon HS. A two-phase linear regression model for biologic half-life data. Journal of Laboratory and Clinical Medicine. 1990;115(6):745-748.

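### SAP 9.2 labels as CL and steady-state volume what SC-only washout data can identify only as CL/F and Vz/F, and it does not define the AUC behind them

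*SAP*

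**What the plan says.** SAP 9.2 lists two parameters of interest here: "clearance (CL) (from Day 28 and subsequent samples during washout" and "volume of distribution at steady state (Vz) (from Day 28 and subsequent samples during washout". The terminal half-life has its own semiparametric method. For the rest, "Other parameters will be calculated using a standard non-compartmental approach". The opening paragraph of SAP Section 9 speaks more broadly of "compartmental and non-compartmental analysis in Demitasse 2000", but no compartmental model is specified.

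SAP Section 13 explains the departures from the protocol's parameter list. Of AUC, Cmax and Tmax it says that the protocol requires their derivation, "which is not possible due to limited sampling and nature of the study". It adds that "CL and Vd will only be possible to derive for Day 28 and subsequent samples during the washout period".

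The volume therefore has three names: steady-state volume, Vz and Vd. The glossary repeats the first pairing. No bioavailability term, no /F label and no formula for CL or V appears in SAP 9.2, the summary table in 9.3.3 or the glossary. The note-to-file rows that are available do not change 9.2.

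**The concern.** There are three linked problems.

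- **Identifiability.** Concentrations after SC dosing depend on the absorbed dose, F × dose. Without F they give CL/F and V/F only. F cannot be recovered within this study, because a single post-IV sample, at about 35 minutes, is taken before SC dosing starts.
- **Wrong volume.** Vz is clearance divided by the terminal slope. It equals Vss only under one-compartment kinetics, whereas SAP 9.2 itself refers to a beta phase and cites a two-phase model.
- **Undefined AUC.** Non-compartmental clearance is dose divided by an AUC. Section 13 dismisses AUC without saying which AUC will stand behind CL. The stated window runs from Day 28 through washout, so two analysts could choose different intervals and print very different numbers.

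Describing the PK of the SC regimen is the first secondary objective. A reader who takes the printed value as systemic clearance, compares it with IV clearance, or applies F to it again will go wrong by a large factor.

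**Working it through.** The documents state no CL or V figure, so there is nothing to reproduce. The check covers what the labels would imply.

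**Inputs**
- Dosing (SAP 3.7): one IV dose of 50 IU/kg on Day 1, and 28 daily SC doses of 100 IU/kg, so the dosing interval is 24 h.
- Samples in the window (SAP 9.1): Day 28 pre-dose, then Days 29 to 33.
- F (Protocol 2.2.2): "Single-dose bioavailability was 18.2-23.6"%. The same section says that the IV load increased SC bioavailability, but gives no figure.
- Half-life (Protocol 2.2.2): 63.2 h after repeated SC dosing (interquartile range 60.2 to 64.0); 66 to 103 h after a single SC dose. Tmax is 6 to 24 h.

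**Step 1: is the window SC-only?** The fraction of the IV dose left at Day 28 (27 × 24 = 648 h) is 2^(−648/t½):
- t½ 63.2 h: 0.08%
- t½ 103 h: 1.3%

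In effect, yes. By the same calculation, the regimen has reached 99.9% and 98.7% of steady state.

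**Step 2: size of the missing F.** At steady state, dose / AUC over the interval = CL/F, and Vz/F = (CL/F) / terminal slope. Reading either as systemic multiplies it by 1/F.

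| F | 1/F |
|---|---|
| 23.6% (protocol) | 4.24 |
| 18.2% (protocol) | 5.49 |
| 40% (assumed) | 2.5 |
| 30% (assumed) | 3.3 |

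The assumed rows show the effect if the IV load raised F.

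**Step 3: size of the AUC choice.** If the last single dose is divided by the AUC from Day 28 to infinity, that AUC also contains residue from the 27 earlier SC doses. Under one-compartment kinetics at steady state, CL/F is then understated by the accumulation ratio R = 1 / (1 − 2^(−24/t½)):
- t½ 60.2 h: 4.14
- t½ 63.2 h: 4.32
- t½ 66 h: 4.49
- t½ 103 h: 6.71

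**Step 4: both together.** The printed value relative to true CL is (1/F)/R. Over the protocol's F range and half-lives of 60.2 to 103 h, this runs from 4.24/6.71 = 0.63 to 5.49/4.14 = 1.33. The two errors largely cancel.

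**Step 5: what remains with the interval AUC.** Day 28 pre-dose and Day 29 are both troughs, so a trapezoid between them misses the SC peak. A one-compartment simulation was run with first-order absorption, Tmax of 6, 12 or 24 h, half-life of 63.2, 66 or 103 h, F assumed 0.20, and the planned dosing and sampling. It gave CL/F overstated by a factor of 1.04 to 1.13. If that value were then also read as systemic CL, the worst case would be 5.49 × 1.13 = 6.2.

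**The case against.** The strongest reply is that this is only labelling. SAP 4.3 ties the endpoints to the SC regimen, 9.2 names the source samples, and a pharmacokineticist will read CL as CL/F. For projecting one SC dose from another, CL/F is the right quantity (SC dose rate = CL/F × average level), so a value used that way gives no error. That stands, and it limits the harm to readers who treat the value as systemic or apply F again.

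It can also be said that Section 13 drops the protocol's AUC from 0 to t and 0 to infinity, not every AUC. Dose over the interval AUC is an ordinary reading of a non-compartmental method at steady state, and the Day 28 and Day 29 samples can approximate it. This stands in part: CL/F is derivable. But the SAP does not say so, and its text on AUC points the other way.

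The F range is from single doses, and every subject here receives an IV load that the protocol says raised bioavailability. This also stands, so the 4.2- to 5.5-fold figure is conditional.

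Two stronger readings are tempting. A reader might join the ranges into one error of roughly 4- to 7-fold. The documents do not support that. The upper end comes only from an AUC that the SAP never says it will use, that error runs the other way, and it is measured against CL/F. Reaching 7 through F alone needs F = 1/7 = 14.3%, below every figure quoted. A reader might also infer that the mislabelled clearance feeds directly into dose selection for later studies. No section uses CL or V for that. The dosing guidance in SAP 3.5 rests on steady-state activity above 12%, and the primary endpoint in 8.1 uses measured activity.

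**Conclusion.** The point holds as one of labelling and definition. SAP 9.2 names parameters that the design cannot identify, pairs a steady-state description with a terminal-phase symbol, and relies on a method that needs an AUC while Section 13 rules AUC out.

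Read as systemic values, CL and V would be overstated 4.2- to 5.5-fold if single-dose F applies. The factor is smaller if the IV load raised F. The separate risk from an undefined AUC is a 4.3- to 6.7-fold understatement of CL/F for half-lives of 63.2 to 103 h. It assumes one-compartment kinetics at steady state, and an analyst choosing the infinite AUC. These figures are alternatives with opposite signs, not a combined range.

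The consequence is confined to secondary, descriptive PK parameters in a six-subject, non-inferential study. The primary endpoint is unaffected.

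**What to change.** - In SAP 9.2, 9.3.3, Section 13, the glossary, Table 14.2.2.2.1 and Listing 16.2.6.2, label the parameters CL/F and Vz/F. Remove the steady-state description from Vz and drop the synonym Vd.
- In 9.2, define CL/F = dose / AUC over the Day 28 to Day 29 dosing interval, and Vz/F = (CL/F) / terminal slope.
- In Section 13, say that this interval AUC is used, and that absolute CL and Vss are not estimable from the planned samples.
- Add a footnote that an interval AUC from two troughs misses the SC peak and so overstates CL/F modestly, by about 4 to 13% in a one-compartment simulation.

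The cost is SAP wording and output labels, with no new samples or visits. The reported parameters become less ambitious, but they are ones that the design can deliver.

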9.3. Presentation of Concentration Data

9.3.1. Handling of Missing Data

Missing concentration and activity data for all subjects who are administered scheduled study treatments will be considered as non-informative missing and will not be imputed. No concentration estimates will be provided for missing sample values.

For the derivation of PK parameters, the following rules will apply:

- Concentration values below the assay's lower limit of quantification (BLQ) in pre-dose samples and in samples taken before the time of the first quantifiable concentration will be treated as zero;
- The sampling time of pre-dose samples relative to dosing will also be treated as zero;
- Post-dose BLQ values after the first quantifiable time point will be treated as zero.
- If the actual time of sampling is missing, the planned time may be used.

For PK concentration and activity summary, individual concentration versus time curves the following rules will apply:

This document is confidential.

Statistical Analysis Plan for Interventional Studies
Sponsor: Catalyst Biosciences, Inc.; Protocol No.: DLZ-201

- PK concentrations BLQ in pre-dose samples and in samples taken before the time of the first quantifiable value will be set to zero;
- The PK concentrations BLQ after quantifiable concentration will be set to zero.

No further imputation will be applied to any missing values.

9.3.2. Listing and Presentation of Individual PK Data

Individual PK FIX activity levels and actual sampling time of PK blood sample collection will be listed for each subject for treatment period and washout period and will include the deviation in time from the scheduled time, if applicable. Subjects with protocol deviation affecting PK may be flagged and excluded from PK Population.

Individual subject intense PK parameters will be listed for the Safety population. Unreliable PK parameters will be listed but flagged and excluded from summary by PK Specialist.

The following figures will be produced:

- Individual intense PK concentration-time provided for FIX activity levels with all subjects in the same figure on linear scales.

9.3.3. Summary of PK Concentrations and Parameter in Plasma

The PK concentration for FIX activity level will be summarized overall and will be based on actual dose administration.

PK parameters and activity level will be summarized by time point using the following descriptive statistics:

Variable	Summarized with:
PK FIX activity level at each nominal time point	n Number and %BLQ mean +/- SD Coefficient of variance (CV) [%] median ± IQR Min - Max
CL, Vz	n mean +/- SD CV [%] median ± IQR Min – Max GM (GCV)
Washout period t1/2	n mean +/- SD CV [%] median ± IQR Min - Max

Note: GM = geometric mean, GCV = geometric CV [%]

CV [%] = SD/mean in %

IQR = 3rd Quartile – 1st Quartile

%BLQ = total number of subjects who have BLQ values / total number of subjects at each time point in %

This document is confidential.

Statistical Analysis Plan for Interventional Studies
Sponsor: Catalyst Biosciences, Inc.; Protocol No.: DLZ-201

Mean concentrations, SD, and CV will not be presented if 70% or more of the actual values at any time point are BLQ or missing.

9.4. PK Parameters Derivation: Attainment of Steady State for FIX Activity

Attainment of steady state will be estimated using aggregate assessment of trough concentration if sufficient data will be available.

To assess whether steady state was achieved for FIX activity after daily dosing of CB2679d, aggregate assessment of trough concentration will be used to evaluate attainment of steady state (Maganti et al 2008). The approach is based on the comparison of log-transformed normalized trough concentration values for each dose to the mean of the results for all the following doses.

This analysis will be done using repeated measures analysis only if the data are sufficient to support; i.e., analysis will be carried out only on subjects who have at least 3 valid FIX activity level results out of 6 pre-dose samples). Alternatively, analysis of variance (ANOVA) comparison will be carried out on log-transformed Cmin (concentration at the end of the dosing interval = FIX activity level pre-dosing) pre-dose on days 2, 3, 7, 14, 21 and 28. The following SAS code may be used to conduct the analysis:

PROC MIXED;

CLASS <time> <subject>;

MODEL log_base_e_ <FIX actual level> = <time> /DDFM = KR;

LSMEANS <time>;

RUN;

The DDFM = KR (Kenward Roger) option performs the degrees-of-freedom calculations detailed by Kenward and Roger (1997).

Contrasts will be tested between a time point and the pooled mean over all remaining time points. For example, the following contrasts will be tested as example:

- Day 3 vs Days 7, 14, 21, and 28
- Day 7 vs Days 14, 21, and 28
- Etc.

The first non-significant comparison will be concluded to be the dosing interval at which steady state concentration are attained. The p-value for difference of Least Square Means (LSM), Geometric Mean Ratio, and the 95% confidence interval (CI) for the contrasts will be provided.

This document is confidential.

Statistical Analysis Plan for Interventional Studies
Sponsor: Catalyst Biosciences, Inc.; Protocol No.: DLZ-201

10. Analysis of Pharmacodynamics

PD analysis will be performed using SAS statistical package version 9.4 or higher. PD analysis will be performed for PD and Safety Population.

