3.5. Determination of Sample Size

Six (6) subjects are sufficient to provide guidance on range of dose required to achieve steady-state activity >12% and starting SC dose for subsequent studies. As this study is not inferential, no formal sample size calculation is required.

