4.1. Primary Efficacy Endpoint

The primary endpoint is:

- Number of subjects who achieve a steady-state FIX activity level above 12% with daily dosing.

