6.2.1 Baseline and Change from Baseline	Maximum absolute change from baseline will be calculated as the maximum of the absolute changes from baseline over all visits during treatment period.	Maximum change from baseline will be calculated as the maximum of the changes from baseline over all visits during treatment period.
8.2.1 Change in FIX levels from pre-dose	Actual and change from baseline (including maximum absolute change from baseline) values for FIX activity level will be summarized by time point for the PK and the Safety Population. Different PK parameters will be summarized as well as described in Section Error! Reference source not found.	Actual and change from baseline (including maximum change from baseline) values for FIX activity level will be summarized by time point for the PK and the Safety Population. Different PK parameters will be summarized as well as described in Section Error! Reference source not found.
9.3.2 Listing and Presentation of Individual PK Data	The following figures will be produced: Individual intense PK concentration-time provided for FIX activity levels with all subjects in the same figure on linear scales.	The following figure will be produced: Box plots of PK concentration provided for FIX activity levels by visits.
9.3.3 Summary of PK Concentrations and Parameter in Plasma		Added: Geometric CV = sqrt (exp ((log (geometric SD)) ^2) - 1) * 100%
9.4 PK Parameters Derivation: Attainment of Steady State for FIX Activity		Added: REPEATED <time> /type = un SUBJECT = <subject>
10.2 PD Biomarkers Analysis	Actual and change from baseline (including maximum absolute change from baseline) for all PD parameters (e.g., Prothrombin Time, aPTT, Fibrinogen, D-dimer, F1+2, and TAT) will be summarized by time point. Coagulation assays and thrombogenicity markers will be tabulated separately.	Actual and change from baseline (including maximum change from baseline) for all PD parameters (e.g., Prothrombin Time, aPTT, Fibrinogen, D-dimer, F1+2, and TAT) will be summarized by time point. Coagulation assays and thrombogenicity markers will be tabulated separately. Added: In case that thrombogenicity markers are below limit of quantification, then all analysis are done with the imputed midpoint of the potential values

This document is confidential.

Note to File, 24-July-2020
Sponsor: Catalyst Biosciences; Protocol No.: DLZ-201

Section	Revised from	Revised to

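### The primary endpoint counts subjects at steady state above 12% FIX, but the plan has no rule that decides steady state for a subject, and the group test in SAP 9.4 cannot supply one

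*SAP*

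**What the plan says.** SAP 4.1 defines the primary endpoint per subject: "Number of subjects who achieve a steady-state FIX activity level above 12% with daily dosing". Protocol 9.1 and 9.4.2 (Version 2.0) agree.

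SAP 8.1 puts this into practice as the number and percentage of subjects with FIX above 12% in the treatment period, for the PK and Safety Populations. It names no day, does not restrict the count to pre-dose troughs, and does not refer to SAP 9.4. The assessments it lists include the Day 1 sample taken 35 minutes after the IV load. The titles of Tables 14.2.1.1 and 14.2.1.2 drop the words steady state.

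SAP 9.4 holds the only steady-state method. It states that "aggregate assessment of trough concentration will be used to evaluate attainment of steady state" and compares the mean log trough on one day with the mean over the later days. Its decision rule is: "The first non-significant comparison will be concluded to be the dosing interval at which steady state concentration are attained". The result is one dosing interval for the cohort. The code printed in SAP V1.0 has no REPEATED statement; the Note to File adds one with an unstructured covariance.

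The Note to File also replaces the individual FIX profiles of SAP 9.3.2 with this: "Box plots of PK concentration provided for FIX activity levels by visits".

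**The concern.** An endpoint worded per subject needs a rule applied per subject. Here one section counts subjects without testing for steady state, and another tests for steady state without looking at subjects. A subject who is above 12% on Day 7 and has lost activity by Day 28 is not excluded from the primary count by anything in the text.

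Such a loss is plausible. Protocol 2.2.2 reports neutralizing antibodies in both subjects of the earlier cohort given IV plus SC dosing, the route sequence used here. The count is meant to guide later work: "Six (6) subjects are sufficient to provide guidance on range of dose required", together with the starting SC dose for subsequent studies. An inflated count would make the tested regimen look more reliable than it was.

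**Working it through.** **Inputs.** n = 6 and trough days 2, 3, 7, 14, 21 and 28 (SAP 3.5, 9.4). Two-sided alpha of 0.05 is an assumption, drawn from the statement that the "Geometric Mean Ratio, and the 95% confidence interval (CI) for the contrasts will be provided". The plan gives no power or error figure for this test, so there is nothing of its own to reproduce.

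**Step 1: the count in SAP 8.1.** Suppose all six subjects exceed 12% at some early sample and two later fall below it. Counting any value above 12% gives 6/6 = 100%. Requiring the level to be held gives 4/6 = 67%.

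Early values above 12% are likely. In the earlier IV-plus-SC cohort the nadir was 20% in both subjects (Protocol 2.2.2; that cohort's doses are not in the text). With the 63.2 h half-life from the same section, and assuming single-exponential decay, the share of the load remaining is:
- Day 2 pre-dose: 2^(−24/63.2) = 0.77
- Day 14 pre-dose: 2^(−312/63.2) = 0.03

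At the longest single-dose half-life quoted, 103 h, these become 0.85 and 0.12. Early troughs carry the load; Day 14 onward mostly does not.

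**Step 2: SAP 9.4 under the Note to File covariance.** With complete data and an unstructured covariance, each contrast is a paired t test on 5 df. Let k of 6 subjects have contrast value d and the rest 0:
- mean = kd/6
- SD² = d²k(6−k)/30, so SE² = d²k(6−k)/180
- t = mean/SE = √(5k/(6−k)), in which d cancels

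| k | t | p (5 df) |
|---|---|---|
| 1 | 1.00 | 0.363 |
| 2 | 1.58 | 0.175 |
| 3 | 2.24 | 0.076 |
| 4 | 3.16 | 0.025 |

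The critical value is 2.57. A larger fall in the same subjects does not help, because it inflates the variance of the contrast along with its mean.

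**Step 3: does this hold under other covariances?** Take equal loss from Day 14, flat troughs before it, and no noise. The residual variance is d²k(6−k)/60 on 30 df with independent errors (SAP V1.0 code) and d²k(6−k)/100 on 25 df with compound symmetry. The Day 7 contrast then gives t² = 7.5k/(6−k) and 12.5k/(6−k). The Day 2 contrast gives 3k/(6−k) and 5k/(6−k).

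| Structure | k | p, Day 2 vs later | p, Day 7 vs later |
|---|---|---|---|
| Unstructured | 2 | 0.175 | 0.175 |
| Unstructured | 3 | 0.076 | 0.076 |
| Independent | 2 | 0.230 | 0.062 |
| Independent | 3 | 0.094 | 0.010 |
| Compound symmetry | 2 | 0.126 | 0.019 |
| Compound symmetry | 3 | 0.035 | 0.002 |

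So the result depends on the covariance and on the day examined.

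**Step 4: is 3 a ceiling?** No. With all six subjects lost from Day 14 or Day 21 (simulated, flat before and after, assumed log SD 0.1 to 0.3), a contrast after the loss is non-significant and steady state is declared at the floor level in about 93–100% of runs.

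**Step 5: limits of steps 2 to 4.** They need positive values. SAP 9.3.1 sets BLQ results to zero, which has no logarithm, so complete loss recorded as BLQ would leave the model. In addition, six complete subjects at six times leave 5 residual df for a 6×6 unstructured matrix of 21 parameters. The estimate is singular, and the model may not fit as specified.

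**The case against.** The strongest reply is that SAP 9.4 does no harm to the primary result, because it feeds nothing into it. SAP 8.1 never cites 9.4, and 9.4 classifies no subject. That is correct, and it rules out a tempting inference: that the group test declares steady state in subjects who lost activity and so inflates the count. The inflation comes from 8.1 alone. If 9.4 rejected correctly every time, 8.1 could still give 6/6.

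A second tempting inference is that 9.4 can never react when up to three of six subjects lose all activity. Step 3 shows contrasts that do reject at two or three, step 4 shows that three is not a limit, and step 5 shows that total loss may not enter the model at all.

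Third, individual loss is not hidden. FIX values are listed by subject (SAP 9.3.2, Listing 16.2.6.1), minimum, maximum and %BLQ are tabulated by time point (SAP 9.3.3), and antibody results are listed with titers (SAP 11.8). The box plots remove a convenient display, not data. This stands, but a listing does not decide who counts.

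Fourth, the protocol attributes the earlier antibodies mainly to a 3-month gap in dosing, so they are weak evidence on how often loss will occur here. They still make it a case the rule should handle.

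Finally, the plan is descriptive: "As this study is not inferential, no formal sample size calculation is required". That excuses the absence of a power calculation. It does not excuse an endpoint whose numerator is undefined.

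**Conclusion.** The concern holds as a gap in definition. The primary endpoint is per subject, and no section decides steady state for a subject. The consequence is a primary count that can be too high. In the two-subject illustration it reads 6/6 rather than 4/6, which assumes that both subjects exceed 12% early and fall below it later. SAP 9.4 cannot fill the gap, because it describes the group mean and reads non-significance with six subjects as attainment. The p-values of 0.36, 0.17 and 0.076 illustrate this for one paired contrast under the unstructured covariance, with equal falls and complete positive data; they do not describe the plan under every model or pattern of loss. This should be corrected. The samples needed are already scheduled.

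**What to change.** - **SAP 8.1.** Count a subject as a success only if his own Day 14, 21 and 28 pre-dose troughs under daily dosing are all above 12%. A trough that is missing, BLQ or lost to a dosing interruption does not count as success; list the reason beside each non-success.
- **Description of stability.** List each subject's ratio of the Day 28 trough to the geometric mean of Days 14 and 21. Do not attach a 25% pass/fail limit borrowed from the protocol's retest trigger. That text leaves open whether 25% is relative or 25 IU/dL, and a limit on falls alone ignores troughs that are still rising. It would also fail stable subjects through noise, with probability Φ(ln 0.75/(SD√1.5)) = 0.009, 0.059 and 0.120 at assumed log SD 0.1, 0.15 and 0.2. At least one of six stable subjects would then fail in 1 − (1 − p)^6 = 5%, 31% and 54% of trials. If the sponsor wants a margin, it should be two-sided and justified.
- **SAP 9.4.** Label the contrast as a supportive description of the group mean that does not establish steady state in any subject.
- **SAP 9.3.2 and Note to File.** Restore the individual FIX profile figure beside the box plots.

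The cost is SAP wording, one derived flag per subject and one figure, with no new samples. The count may come out less favourable, and three troughs above 12% show that the level was held, not that it was flat; the listed ratio is there for that.
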